6 ANALYSIS POPULATIONS

Full Analysis Set (FAS): consists of all enrolled subjects who received at least one dose of investigational product during the study.

Full Analysis Set – SF-10 (FAS – SF-10): consists of the subset of subjects in the full analysis set who had a non-missing baseline.

Full Analysis Set – SF-12v2 (FAS – SF-12v2): consists of the subset of subjects in the full analysis set who had a non-missing baseline.

7 DATA SCREENING AND ACCEPTANCE

7.1 General Principles

Data will be reviewed periodically and any questionable data will be reported to the clinical data manager promptly for query and resolution.

7.2 Handling of Missing and Incomplete Data

Missing clinical outcome data can occur for multiple reasons, including missed subject visits and scales or measures with missing item scores. Missing and incomplete data will be identified through the data quality review plan for this study. Missing and incomplete data will be identified for investigation, and possible resolution, by Data Management prior to the study database lock or snapshot.

Unless specified otherwise, only the observed data (not imputed data) will be presented in listings.

For efficacy analyses related to seizure diary or EEG, the following imputation rules will be applied for subjects with incomplete diary/EEG data,

- For subjects who have incomplete diary data, observable/absence seizure frequency will be calculated by averaging over the days with complete diary data during the corresponding visit period.
- For subjects who have incomplete EEG, absence/non-absence seizure frequency will be calculated by averaging over the time that is complete during the corresponding visit time, even if the EEG is not done overnight.

7.2.1 Missing Date of the Last Dose of Investigational Product

When the date of the last dose of investigational product is missing for a subject, all efforts should be made to obtain the date from the Investigator. If after all efforts are made it is still missing, the last visit date will be used as the last dose date.

7.2.2 Missing Medical History Related Dates (eg, diagnosis date) or Birth Dates

- If only day is missing, impute 1.
- If month is missing, impute January 1st.
- If year is missing, then no imputation will be done; the date will be missing.

If the imputed date is earlier than the birth date, then the birth date will be used.

7.2.3 Missing Date Imputation for Adverse Events and Concomitant Medications

The following conventions will be used to impute missing portions of dates for adverse events and concomitant medications. Note that the imputed values outlined here may not always provide the most conservative date.

Missing Start Dates

- If the day is unknown, then:
 - If the month and year match the first dose of investigational product start date month and year in this study, then impute the day of the first dose date.
 - Otherwise, assign the first day of the month.
- If the month is unknown, then:
 - If the year matches the year of the first dose of investigational product date in this study, then impute the month and day of the first dose date in this study.
 - Otherwise, assign ‘January’
- If the year is unknown, then the date will not be imputed and will be assigned a missing value.

If the imputed date is earlier than birth date, then birth date will be used. If the imputed start date is later than the end date, then the start date will be set as the same date as the end date.

Missing Stop Dates and not ongoing

- If the day is unknown, then assign the last day of the month.
- If the month is unknown, then assign ‘December.’
- If the year is unknown, then the date will not be imputed and will be assigned a missing value, and the event will be considered ongoing. If the AE has been recorded as resolved/recovered, all efforts should be made to obtain the date from the Investigator.

If the resulting end date is after the date of study completion / discontinuation/ data cutoff, set the imputed end date as close to the date of study completion / discontinuation/ data cutoff as possible without overwritten existing information

If the year is missing for the start date, and stop date (observed or imputed) is on or after the first dose or event is ongoing. The start date will be imputed as the first dose date.

7.2.4 Missing Causal Relationship to Investigational Product for Adverse Events

If the causal relationship to the investigational product is missing for an AE that started on or after the date of the first dose of investigational product, a causality of “definitely related” will be assigned. The imputed values for causal relationship to investigational product will be used for the incidence summary; the values will be shown as missing in the data listings.

7.2.5 Visit Time Windows

For all scheduled efficacy and safety assessments except seizure diary, the visit window assigned and the corresponding target treatment days during which an actual visit may occur is specified in Table 3.

Termination visit for subjects who didn't complete the study, and unscheduled visits will be mapped to the closest post baseline scheduled visits if the scheduled visits are missing. If there are more than one unscheduled/end of study visits mapped to the same window, the one closer to the target day will be used. If more than one visit has the equal distance to the target day then the later one will be used, if more than one visits on the same day, use the time or the sequence number to select the later record. For listings and shift tables, all data points will be included. For assessments where both the planned study visit and an unscheduled visit or early termination visit corresponding to that study visit are both available, the planned study visit will be used for the analysis.

In general, all summary tables by visit include all scheduled assessments per schedule of assessments. For seizure diary data to measure, it will be mapped to time period between the visit time points as specified in Table 4 and will be used to define observable seizure frequency (refer to Section 5.8.1). If a subject misses a visit, then the expected visit date will be used in place of the actual visit date to define observable seizure frequency. Expected visit date is the date of the previous visit + the expected number of days between the previous visit and the missing visit. If the previous visit is also missing, then the expected date of the previous visit would be used instead.

Table 3: Visit Time Windows for Scheduled Efficacy and Safety Assessments

Period	Visit	Scheduled Visit Day	Window
Treatment Year 1	Month 0	Day 1	Days ≤ 1
	Month 3	Day 92	Days [2, 138]
	Month 6	Day 184	Days [139, 230]
	Month 9	Day 276	Days [231, 322]
	Month 12	Day 368	Days [323, 414]
Treatment Year 2 - 3	Month 18	Day 552	Days [507, 598]
	Month 24	Day 736	Days [691, 782]
	Month 30	Day 920	Days [875, 966]
	Month 36	Day 1104	Days [1059, 1150]

*Number of days in 3-month visit period = $(365.25/12) * 3 \approx 92$ days

Table 4: Visit Time Windows for Seizure Diary

Period	Visit Period	Scheduled Visit Day	Window*
Treatment Year 1	Month 0 – 3	Day 1 – Day 92	Days \leq 1 – Study Day of Month 3 visit
	Month 4 – 6	Day 93 – Day 184	Study day of Month 3 visit + 1 – Study day of Month 6 visit
	Month 7 – 9	Day 185 – Day 276	Study day of Month 6 visit + 1 – Study day of Month 9 visit
	Month 10 – 12	Day 277 – Day 368	Study day of Month 9 visit + 1 – Study day of Month 12 visit
Treatment Year 2 - 3	Month 13 – 18	Day 369 – Day 552	Study day of Month 12 visit + 1 – Study day of Month 18 visit
	Month 19 – 24	Day 553 – Day 736	Study day of Month 18 visit + 1 – Study day of Month 24 visit
	Month 25 – 30	Day 737 – Day 920	Study day of Month 24 visit + 1 – Study day of Month 30 visit
	Month 31 – 36	Day 921 – Day 1104	Study day of Month 30 visit + 1 – Study day of Month 36 visit

*refer to [Table 3](#) for visit window of each visit time point.

Study Day is calculated as (visit date – date of the first dose in UX007G-CL202 study + 1), if visit date is on or after the date of the first dose in UX007G-CL202 study; and as (visit date – date of the first dose), if visit date is before the date of the first dose in UX007G-CL202 study.

7.3 Testing/Validation Plan

Data will be reviewed by cross functional team periodically and issues will be addressed by clinical data management.

7.4 Software

SAS® software version 9.4 or higher will be used to perform statistical analyses unless otherwise specified.

8 STATISTICAL METHODS OF ANALYSES

8.1 General Principles

All statistical tests will be two-sided and tested at statistical significant level of 0.05. The statistical analyses will be reported using summary tables, figures, and data listings. Continuous variables will be summarized by number of subjects and mean, standard deviation (SD), median, minimum, and maximum values. Categorical variables will be summarized by number and percentage of subjects. All raw data obtained from the CRFs will be included in data listings. In general, analysis will be performed for Rollover subjects and Non-Rollover subjects, separately.

8.2 Subject Accountability

The number and percentage of subjects in the Full Analysis Set, Full Analysis Set – SF-10 and Full Analysis Set – SF-12v2 will be summarized by subject group and subject seizure type. Subjects excluded from the analysis sets will be listed. The number and percentage of subjects who complete the study, and who prematurely discontinue will be presented. The reasons for premature discontinuation from treatment as recorded on CRFs will be summarized as well.

8.3 Protocol Deviations

Protocol deviations will be summarized for the Full Analysis Set. Both major and minor protocol deviations will be listed.

8.4 Demographic and Baseline Characteristics

For all subjects, age at informed consent in UX007G-CL202 study will be presented. Other demographic parameters (e.g., gender, race, ethnicity and age at Glut1 DS diagnosis) and other baseline characteristics measured at baseline of the feeder study will be used for Rollover subjects. For Non-Rollover subjects, demographic and other baseline characteristics measured at the baseline of UX007G-CL202 study will be used.

8.5 Disease Characteristics and Medical History

Summary statistics will be presented for the Full Analysis Set, for the following parameters:

- Duration of Glut1 DS symptom
- Glut1 DS mutation description
- Glut1 DS symptoms history including whether ongoing
- Ketogenic Diet (KD) history and reason for KD discontinuation
- Seizure history by type
- Average number of observable seizures per month over the last 6 months

For Rollover subjects, medical history recorded at the baseline of the UX007G-CL201 study and the current study will be used. For Non-Rollover subjects, medical history recorded at in the current study will be used.

8.6 Prior and Concomitant Medication

For Rollover subjects, prior medication will be defined as any medication taken before the first dose in the UX007G-CL201 study. For Non-Rollover subjects, prior medication will be defined as any medication taken prior to the first dose of UX007 in the current study.

Concomitant medication is defined as any medication taken during the study between the day of the first dose of the investigational product and the day of the last dose of the investigational product in UX007G-CL202 study. A medication started before the date of the first dose of investigational product and also taken after the date of first dose of investigational product will be counted both as a prior and concomitant medication.

Both prior and concomitant medications will be coded by drug name and therapeutic class using World Health Organization (WHO) Drug Dictionary. The number and proportion of subjects receiving each reported prior and concomitant medication will be summarized by Anatomical Therapeutic Chemical (ATC) code and preferred term for the Full Analysis Set. Multiple uses by a subject of the same drug will be counted only once in the summary tables.

8.7 Investigational Product Administration

8.7.1 Extent of Exposure

Exposure duration to UX007 will be summarized for the Full Analysis Set.

8.7.2 Measurement of Treatment Compliance

Number of days during a visit period is calculated as (end of visit period date – start of visit period date + 1). Percent of days missed for a period is $100 \times (\text{number of days during the visit period with dose non-compliance}) / (\text{number of days during the period})$. Descriptive statistics for dosing compliance will be summarized. Number and percent of days with missing dose will also be summarized.

8.7.3 Diet Diary Review

The following measures will be summarized by visit based on the 3-day Diet Diary Review:

- Average Study Drug Calories, as calculated as the average of the 3 entries for study drug
- Average Total Daily Calories

8.8 Efficacy Analysis

Because the primary objective of this study is to evaluate the long-term safety, the efficacy parameters will not be grouped into primary or secondary categories. Efficacy analyses will be based on the Full Analysis Set.

- Seizure frequency

For Rollover subjects, frequency of seizures (normalized to a 4-week rate) up to first year will be analyzed using generalized estimating equations (GEE), with reduction from baseline for each visit period (see Section 7.2.5, Table 4) as the response variable, baseline as covariates, visit period (in UX007G-CL202 study) as a factor, identity link function and exchangeable within subject working correlation matrix.

Frequency of seizures will be derived for each subject based on subject seizure type. Observable seizures from the diary will be used for Observable Seizures Subjects. For Absence Seizures Only Subject, the absence EEG data measured at the scheduled visit (matching the each period end time specified for seizure diary, see Section 7.2.5, Table 4) will be used, e.g., scheduled Month 3 EEG absence seizure data will be used to assess seizure frequency for visit period Month 0 – 3.

For Non-Rollover subjects, descriptive statistics of observed value will be presented.

- Seizure frequency from diary

For Rollover subjects, observed value and reduction from baseline in frequency of observable seizure and absence seizure (normalized to a 4-week rate) for each visit time period (see Section 7.2.5, Table 4) will be summarized by subject group and subject seizure types.

For Non-Rollover subjects, descriptive statistics of observed value will be presented.

- Seizure frequency from EEG

For Rollover subjects, observed value and reduction from baseline in frequency of absence seizure and non-absence seizure (normalized to a 24-hour rate) for each visit time point (see Section 7.2.5, Table 4) will be summarized by subject group and subject seizure types.

For Non-Rollover subjects, descriptive statistics of observed value will be presented.

For Rollover subjects, descriptive statistics for observed value and change from baseline will be presented by assessment time point for the following endpoints:

- CNS total score
- SF-10 summary scores
- SF-12 domain/summary score

For Non-Rollover subjects, descriptive statistics of observed value will be presented.

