7.2 Discussion of Study Design, Including Choice of Control Group

UX007G-CL202 is designed as an open-label, multicenter extension study. The goal of the study is to evaluate the long-term safety of UX007 treatment in Glut1 DS patients while providing continuing treatment for clinical trial participants in an associated Phase 2 study and, at the discretion of the Sponsor, additional subjects who participated in other clinical studies, ISTs, or expanded access/compassionate use treatment programs. The study will also explore maintenance of UX007 effects on clinical features associated with Glut1 DS.

Sample size is limited to subjects who have completed the Phase 2 safety and efficacy study, UX007G-CL201, or, at the discretion of the Sponsor, additional subjects who participated in other clinical studies, ISTs, or expanded access/compassionate use treatment programs. The study is intended to provide the maximum amount of information regarding UX007 long-term safety and efficacy in a diverse Glut1 DS population. Since all subjects will continue to receive the same investigational product, randomization and blinding are unnecessary; study drug will be provided open-label.

Historical data obtained from prior clinical study participation and/or medical records may be used as a comparator for the Treatment Extension Period, enabling those subjects to represent an internal control for assessment of safety and efficacy. While the lack of a parallel control group may introduce difficulties in discerning natural disease progression from treatment effectiveness, a placebo-controlled study of this duration is difficult to conduct and possibly not ethical given the need for ongoing disease management.

Given the chronic nature of Glut1 DS, subjects will be eligible to continue maintenance UX007 treatment for up to 3 years, or until one of the following occurs: the subject withdraws consent, the subject is discontinued from the study at the discretion of the Investigator or Ultragenyx, the study is terminated, or until commercial availability of study drug in a subject's region, whichever occurs first. The treatment duration is intended to provide additional long-term safety information and provide sufficient insight on sustained clinical effects in Glut1 DS patients under a single study protocol.

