7.6 Statistical Methods and Determination of Sample Size

The completeness of the data affects the integrity and accuracy of the final study analysis. Therefore, every effort will be made to ensure complete, accurate and timely data collection, and to avoid missing data. The procedures for handling missing, unused, or spurious data, along with the detailed method for analyses will be presented in the Statistical Analysis Plan (SAP); in general, missing data will be treated as missing unless stated otherwise. The information below is intended as a guide to planned analyses.

The statistical analyses will be reported using summary tables, figures, and data listings. Statistical tests will be one-sided at the $\alpha=0.05$ significance level. All analyses and tabulations will be performed using SAS[®]. Continuous variables will be summarized with means, standard deviations, medians, minimums, and maximums. Categorical variables will be summarized by counts and by percentages of subjects in corresponding categories. For time-to-event data, the Kaplan-Meier estimates will be computed and plotted. Graphical data displays may also be used to summarize the data. All raw data obtained from the CRFs as well as any derived data will be included in data listings. For certain data collected over time, the Generalized Estimating Equation (GEE) may be used as the marginal model approach.

Tests of treatment effects will be conducted at a one-sided alpha level of 0.05 and/or one-sided 95% confidence interval where possible. Each secondary endpoint will be tested independently at one-sided alpha=0.05. No adjustments for multiple comparisons will be performed.

Specific details of primary and secondary endpoints as defined in Section 6.1, and associated analyses will be provided in the SAP.

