5.3 Baseline

For Rollover subjects:

The baseline defined in UX007G-CL201 study will be used for UX007G-CL202 study.

For Non-Rollover subjects:

In general, assessment performed on or prior to Month 0 visit (See Section 7.2.5, **Error! Reference source not found.**) in UX007G-CL202 study will be considered as study baseline for Non-Rollover subjects. The initial baseline (assessment prior to initial dose of UX007) is not available for Non-Rollover subjects.

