5.6 Classification of Observable Seizures and Absence Seizures

Table 1 shows the seizure classifications that are distinguished in the seizure diary, and which are counted towards study inclusion criteria and when deriving the observable seizures endpoints.

Table 1: Seizure Classification by Diary

Seizure Code (Diary)	Seizure Classification	Counted Towards Inclusion Criteria	Counted as Observable Seizure	Counted as Absence Seizure
A	Generalized Tonic-Clonic	X	X	
B	Generalized Tonic	X	X	
C	Generalized Clonic	X	X	
D	Generalized Atonic	X	X	
E	Partial/Focal with Secondary Generalization	X	X	
F	Myoclonic	X	X	
G	Myoclonic (Astatic) Atonic	X	X	
H	Myoclonic Tonic	X	X	
I	Complex Partial/Focal	X	X	
J	Simple Partial/Focal Motor	X	X	
K	Simple Partial/Focal Sensory		X	
L	Simple Partial/Focal Psychological		X	
M	Typical Absence	X [*]		X
N	Atypical Absence	X [*]		X
O	Absence with Special Features (Myoclonic absence)	X [*]		X
P	Absence with Special Features (Eyelid myoclonia)	X [*]		X
Q	Unclassified (Inc. epileptic spasms)			
UNK	Unknown			

[*] Note that for the 3 subjects in UX007G-CL201 study PPD seizure codes MNOP were not counted towards study inclusion criteria because they were randomized prior to the implementation of Protocol Amendment 3.

See Table 2 below for the list of absence seizure types that are counted.

Table 2: Seizure Classification by EEG

Label	Definition	Absence Seizure	Non-absence Seizure
GenTC-BMS	Generalized Tonic-Clonic		X
GenT-BMS	Generalized Tonic		X
GenC-BMS	Generalized Clonic		X
Partial-BMS	Partial		X
AbsenceAwake-BMS	Absence Awake (≥ 10 sec)	X	
AbsenceSleep-BMS	Absence Sleep (≥ 10 sec)	X	
IndetAbsenceAwake-BMS	Indeterminate Absence Awake (3-10sec)	X	
IndetAbsenceSleep-BMS	Indeterminate Absence Sleep (3-10sec)	X	
Myoclonus-BMS	Myoclonus		X

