5.7 Classification of Subjects at Baseline by Seizure Type for Rollover Subjects

For UX007G-CL201 rollover subjects, the classification of subjects defined at randomization during UX007G-CL201 study will be used.

- **Observable Seizures Subject:** a subject who meets any of the following:
 - Observable seizure frequency (types A, B, C, D, E, F, G, H, I, J, K and L; see Section 5.6: Table 2) greater than or equal to 4 during the baseline period.
 - Observable seizure frequency less than 4 at randomization and absence seizure frequency less than 4 during the baseline period
- **Absence Seizures Subject:** a subject who meets any of the following:
 - has seizure types M, N, O or P (see Section 5.6: Table 2) recorded on the seizure diary during the baseline period
 - has absence seizures documented on the screening EEG
 - Absence seizure frequency (see Section 5.6, Table 2 and Section 5.8.2) greater than 0 during the baseline period

All subjects will either be an Observable Seizures Subject, an Absence Seizures Subject, or both. Since there is potential overlap, the following definitions are used to classify enrolled subjects into three mutually exclusive groups:

- **Observable Seizures Only Subject:** a subject who is an Observable Seizures Subject *but not an Absence Seizure Subject*
- **Absence Seizures Only Subject:** a subject who is an Absence Seizures Subject *but not an Observable Seizure Subject*
- **Both Seizures Subject:** a subject who is both an Observable Seizures Subject and an Absence Seizure Subject

Classification by seizure type at baseline is not defined for Non-Rollover subjects since all subjects in UX007G-202 study had prior treatment exposure to UX007 and there is no seizure diary measurement data prior to the initial UX007 treatment for Non-Rollover subjects.

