10 APPENDICES

10.1 Appendix A. Efficacy Endpoint Summary Table

Endpoint	Statistical Method	Analysis Population
Reduction from baseline in frequency of seizures up to first year	GEE	FAS (Rollover subjects)
Frequency of seizures	Descriptive statistics	FAS (Rollover subjects)
Frequency of seizures	Descriptive statistics	FAS (Non-Rollover subjects)
Frequency of observable/absence seizures by seizure diary	Descriptive statistics	FAS
Frequency of absence/non-absence seizures by EEG	Descriptive statistics	FAS
CNS total score	Descriptive statistics	FAS
SF-10 summary scores	Descriptive statistics	FAS – SF10
SF-12 domain/summary score	Descriptive statistics	FAS – SF12v2

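### The SAP's only seizure model measures reduction from a CL201 baseline that was partly selected for being high, so its test against zero is not a 5%-level test of a UX007 effect

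*SAP*

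**What the plan says.** SAP 8.8 models Year 1 seizure frequency in Rollover subjects by GEE "with reduction from baseline for each visit period (see Section 7.2.5, Table 4) as the response variable, baseline as covariates", with visit period as a factor, identity link and exchangeable working correlation. In SAP Appendix A the row "Reduction from baseline in frequency of seizures up to first year" is the only efficacy row with a model; all others are descriptive.

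The reference value comes from the feeder study. SAP 5.3 says for Rollover subjects: "The baseline defined in UX007G-CL201 study will be used for UX007G-CL202 study".

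That baseline has other uses too. SAP 5.7 makes a subject an Observable Seizures Subject if observable frequency was "greater than or equal to 4 during the baseline period", and SAP 8.8 then analyses that subject on diary data. A second branch adds subjects with "Observable seizure frequency less than 4 at randomization and absence seizure frequency less than 4 during the baseline period". SAP 5.6 says Table 1 shows the diary classes "which are counted towards study inclusion criteria and when deriving the observable seizures endpoints". Types A to J are marked for both purposes. The numerical CL201 entry threshold is not given.

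On inference, protocol 7.6 states: "Tests of treatment effects will be conducted at a one-sided alpha level of 0.05 and/or one-sided 95% confidence interval where possible". SAP 8.1 sets two-sided 0.05. Protocol 7.2 allows prior-study data as a comparator, "enabling those subjects to represent an internal control for assessment of safety and efficacy", and warns only that natural progression is hard to separate from treatment effect.

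**The concern.** A single-arm model of reduction has one contrast that can speak to a drug effect: mean reduction against zero. Differences between visit periods cannot, because every period is on UX007. But zero reduction means that the extension rate equals the CL201 baseline rate. That is the same as no drug effect only if the baseline count is an unselected reading of the subject's usual rate.

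Here it is not fully unselected. For subjects classed by the 4-or-more branch, the series analysed is the one that was high in the window later used as the reference. A count that qualified partly by chance tends to be lower next time. Adjusting for baseline does not remove this, and neither document mentions it.

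At stake is the first secondary objective, the long-term effect on seizures. This is the one efficacy result that would carry a p-value. The primary safety endpoint is not affected.

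**Working it through.** The plan states no power, effect size or SD, so there is no figure to reproduce. The check is algebra, then simulation under no drug effect.

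**Who is on which series.** Not being an Observable Seizures Subject requires failing both branches of SAP 5.7: observable below 4, and not (observable below 4 with absence below 4). So an Absence Seizures Only Subject has observable below 4 and absence 4 or more. Outside the fall-through group (below 4 on both), each subject's series is the one that reached 4.

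**Expected reduction.** Let μ be a subject's constant true rate, X the observed baseline and Y a later rate, with E[Y | μ] = μ. Unselected, E[X − Y] = 0. Among those with X ≥ 4, E[X − Y] = E[X − μ | X ≥ 4] > 0.

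**Standard error.** With D = X − Y, averaged over the four periods, and the covariate centred, the adjusted estimate at the mean baseline is simply the mean of D. Its standard error uses the residual variance, Var(D)(1 − r²)/n with r = corr(D, X), instead of Var(D)/n. A noisy baseline makes r positive, so the standard error is too small even without selection: the observed baseline mean is treated as free of error. A small-sample sandwich estimate on skewed counts may add to this; the runs do not separate the two.

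**Simulation inputs.** From the documents: 4-or-more rule, four 92-day periods, alpha 0.05, at most 40 subjects. Assumed, because not given: 6-week baseline; the threshold of 4 read as a 4-week rate; 20 or 36 Rollover subjects; lognormal true rates with median 4, 10 or 30 per 28 days (log-SD 1.0, 1.0, 1.2); overdispersed Poisson counts with 28-day CV 0.3, 0.6 or 1.0; GEE mean evaluated at the mean baseline.

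Results for 36 subjects. Rejection is in favour of UX007, nominal 0.025. Sel means all subjects have baseline ≥ 4.

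| Median | CV | Mean baseline (sel) | Spurious reduction (sel) | GEE, no sel | GEE, sel | Paired t, no sel | Paired t, sel |
|---|---|---|---|---|---|---|---|
| 4 | 0.6 | 11.9 | 1.24 | 0.107 | 0.324 | 0.011 | 0.168 |
| 4 | 1.0 | 13.4 | 2.74 | 0.136 | 0.511 | 0.007 | 0.282 |
| 10 | 0.6 | 20.9 | 0.72 | 0.103 | 0.152 | 0.011 | 0.037 |
| 10 | 1.0 | 23.4 | 2.37 | 0.136 | 0.266 | 0.006 | 0.052 |
| 30 | 0.3 | 64.9 | 0.09 | 0.096 | 0.094 | 0.012 | 0.014 |
| 30 | 1.0 | 71.2 | 1.78 | 0.139 | 0.163 | 0.006 | 0.009 |

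In the first row the spurious reduction is 1.24/11.9 = 10% of baseline; in the fifth it is 0.09/64.9 = 0.1%. At the protocol's one-sided 0.05, the first row gives 0.140 without and 0.397 with selection. Over all scenarios, favourable GEE rejection is 0.094 to 0.511 with selection and 0.072 to 0.156 without.

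**Adding the fall-through group** (both series, SAP 5.7 rule, 36 subjects, CV 0.6; shares assumed):

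| Median | Fall-through | Spurious reduction | GEE | Paired t |
|---|---|---|---|---|
| 4 | 0% | 1.23 | 0.319 | 0.163 |
| 4 | 10% | 1.03 | 0.286 | 0.128 |
| 4 | 26% | 0.60 | 0.201 | 0.064 |
| 10 | 5% | 0.56 | 0.137 | 0.025 |
| 30 | 1% | 0.36 | 0.120 | 0.011 |

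**A second set of assumptions** (one-sample t test, 30 subjects, CV 0.5 to 1.0, medians 3, 6 and 10 per 4 weeks) gives favourable rejection of 17–26%, 5–7% and 2–3% if all subjects are at 4 or more. With 25% fall-through it gives 9–13%, 1.5–2.3% and 0.7–1%.

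**Separating the two causes.** With a baseline from a second window not used for selection, the spurious reduction is within 1% of zero and a paired test rejects 0.032 to 0.057 two-sided. The baseline-adjusted GEE still rejects 0.109 to 0.214. Changing the baseline window alone would not repair it.

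**The case against.** The strongest reply is that no treatment-effect test is planned. SAP 8.8 writes no null, contrast or success criterion and does not rank efficacy endpoints. Protocol 7.6.9 says the study is not powered for treatment comparisons, and the documents speak of maintenance of effect. The randomised feeder study carries the question of efficacy. This stands as a limit on weight. It does not dispose of the point, because protocol 7.6 calls its tests tests of treatment effects and SAP 8.1 attaches a 0.05 level. If no test is meant, the SAP should say so.

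Second, selection at entry is not shown in full. Table 1 lists seizure types, not a number or a window. A reader might infer that 4 or more was required for entry; the second branch of SAP 5.7 shows that it was not. The below-4 absence rule also does not say whether diary or EEG counts apply. If diary counts were used, the selected measure is not the EEG series modelled for Absence Seizures Only Subjects. Both points stand and dilute the bias.

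Third, a reader might infer that false positives at least double unless rates are very high. The documents do not support this: with 25% fall-through the t test is at or below its nominal 2.5% at medians 6 and 10. A reader might also infer that admitting only CL201 completers must have removed those who worsened. No dropout rates or reasons are given, so attrition is only a possible further source of bias.

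Finally, protocol 7.2 does concede the lack of a parallel control, but for natural progression, not for a selected reference value.

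**Conclusion.** The point holds in a limited form. The CL201 baseline is partly selected for being high, so some mean reduction is expected with no UX007 effect, and the GEE p-value does not have its stated 5% level as a test of treatment effect.

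Two causes are at work. Selection matters when typical rates are near 4 per 4 weeks (spurious reduction up to about 20% of baseline) and adds little at rates far above that or with many fall-through subjects. Treating the observed baseline mean as fixed inflates the GEE in every scenario run, including those without selection.

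The size in this trial is unknown: actual rates, the CL201 threshold, baseline length, Rollover number and fall-through share are not in the documents. The conclusion also assumes that the test against zero is the one used for a treatment effect. Nothing here implies that UX007 lacks an effect, only that this test cannot show one at its nominal level.

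**What to change.** In SAP 8.8 and Appendix A, state that the test of reduction equal to zero will not be used as a test of treatment effect. Report the by-period mean reduction as an estimate with an interval that allows for baseline variability, for example from the unadjusted within-subject differences. Label it as uncontrolled change from a selected pre-treatment CL201 baseline in CL201 completers. The label is needed because the wider interval corrects the standard error but not the selection. Reconcile the one-sided level in protocol 7.6 with the two-sided level in SAP 8.1 so that the interval has one stated coverage.

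If an efficacy claim is made, set the estimate beside the change from the same baseline in the CL201 placebo arm over its blinded period, under the same SAP 5.7 series rule. Present it as a supportive reference with its own uncertainty, and state the difference in period length.

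The cost is SAP wording and, for a claim, one added analysis of CL201 data. The reported result will be less favourable and its interval wider. The size and length of the placebo period are not in these documents, so the reference may be imprecise.
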